The transmission potential of SARS-CoV-2 is determined in any particular context by the basic reproduction number ( $R_0$ ) when there is no protective immunity in the population.  $R_0$  will vary with time and context, such as population density, number of contacts and environmental conditions, and is dependent on the period of infectiousness, viral load, and the serial interval. Early data estimated the  $R_0$  for SARS-CoV-2 between 2.0 and 3.4 (Ferretti 2020; Li 2020), higher than that for seasonal influenza (Biggerstaff et al 2014). This is likely in part because of key divergent features from influenza such as pre and asymptomatic SARS-CoV-2 transmission (Ferretti 2020; Kimball 2020; He 2020), near absence of severe disease in young children (Wu et al 2020), and a longer estimated serial interval of 3.96 days (Du Z Emerging Infect Dis 2020). The SARS-CoV-2 average  $R_0$  is also higher than estimated for previous novel viruses, such as influenza H1N1 in the 1918 ( $R_0=1.8$ ) and 2009 ( $R_0=1.6$ ) pandemics (Biggerstaff et al 2014) and SARS-CoV-1 ( $R_0=1-5$ ) (Liu et al 2020).

To date, evidence suggests that in temperate climates between 20 and 50% of infections could be asymptomatic (Mizumoto et al 2020; Bi et al 2020; Kimball et al 2020). Pre-symptomatic shedding is common, with comparable viral load in asymptomatic, pre-symptomatic and clinical cases (Kimball et al 2020). This complicates timely targeted application of interventions since people may not know they are infected and will not behave as if they were. The frequency of asymptomatic infection in sub-Saharan African settings is as of yet unclear, and also may vary by setting. Understanding the proportion of asymptomatic infections and their contribution to the reproduction number is important.

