### 4.2 Selection and recruitment

All households in the HDSS (2108 during the last round in 2019) consenting to participate in the study will be **visited biweekly** by a trained HDSS interviewer, following the same procedures as in routine HDSS rounds, specified in the HDSS protocol (Instituto Nacional de Saude, 2016). We assume the same number of households will consent to participate as in other HDSS rounds. Based on previous experience with the HDSS, we expect the HDSS interviewer to visit 6 households per working day on average.

Household heads, or an adult delegated by the household head, will be asked about COVID-19 consistent symptoms among any consented household member, using a structured questionnaire. If a household member is identified by the household head as reporting any respiratory sign (symptom or lowered peripheral oxygen saturation) or loss of smell or taste, with or without fever, in the last week, i.e. a possible COVID-19 case, this household member will be asked to consent for participating, to respond to a structured questionnaire and to collect a nasal swab sample for SARS-CoV-2 testing. Specimens will be tested for SARS-CoV-2, using RT-PCR (at INS in Marracuene). Possible COVID-19 cases in the HDSS households will be detected through four entry points:

- Biweekly HH visits
- Phone call by patient (when symptoms occur)
- Phone call by study team (as currently done in HDSS)
- HDSS household members presenting as COVID-19 suspected case in healthcare facility

If meeting the COVID-19 admission criteria as per national guidance, the possible COVID-19 case will be referred to the Polana Caniço General Hospital (PCGH), the closest healthcare facility and COVID-19 patient management centre.

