### 5. Study Procedures

#### 5.1 Study/visit schedule

Table 2. Schedule of assessments for population-based surveillance. One row corresponds to two weeks.

we ek	month	Informed consent (1)	Sero- survey	Household visit (2)	Unscheduled visit for swab collection	Case Follow- up outcome (3)	Social mixing & uptake (4)
1	Oct20	x	x	x		x	
3				x	x	x	
5	nov/20			x	x	x	x
7				x	x	x	
9				x	x	x	

11	dec/20			x	x	x	
13			x	x	x	x	
15	jan/21			x	x	x	
17				x	x	x	x
19	feb/21			x	x	x	
21				x	x	x	
23	mar21			x	x	x	
25			x	x	x	x	x
27	apr/21			x	x	x	
29				x	x	x	
31	may21			x	x	x	
33				x	x	x	
35				x	x	x	
37	jun/21			x	x	x	
39				x	x	x	
41	jul/21			x	x	x	
43				x	x	x	
45	aug/21			x	x	x	
47				x	x	x	
49	sep/21			x	x	x	x
51			x	x	x	x	
53						x	
55						x	
TOTAL forms filled*		2800 for household surveillance,2400 for sero-survey,8000 for swab collection	2400*4= 9600	2800*5= 70000	8000	8000	2400*4= 9600
TOTAL samples*			2400*4= 9600		8000		

Type of sample		DBS for serology, collected at home**		nasal swab for PCR, collected at home**		
----------------	--	---------------------------------------	--	---	--	--

DBS = dried blood spot

1 Informed consent for household surveillance (by the household head) and sero-survey (by the selected individual or their caretaker) during baseline visit

2 During baseline visit adapted questionnaire to update population characteristics

3 Only of COVID-19 confirmed cases identified by the surveillance, at 28 and 56 days after symptom onset

4 We plan the social mixing survey rounds each time one month after the sero-survey, to spread the workload. The same participants from the sero-survey are asked to complete the questionnaire

\* estimated, based on the available information at the start of the study; we anticipate 8000 respiratory episodes (possible cases), based on previous data from the HDSS, adjusted for increased frequency of reporting (previous data was recorded during three-monthly rounds)

\*\* both serology testing of DBS and PCR testing of nasal swabs will be carried out at INS Marracuene. DBS samples are collected during pre planned visits, PCR samples when a possible case is identified. Nasal swabs undergo PCR testing the day following sample collection and results are communicated back to the individual (or his/her caretaker) that same day.

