All HDSS households will be visited by a trained HDSS interviewer to present the study and ask for informed consent (i) by the household head for the population-based surveillance and (ii) by the individuals selected for the age-stratified serial sero-survey. During this same visit, if the household head consented, the demographics data (baseline household visit form) will be verified and updated. A study household card with unique IDs of each household member will be provided (code containing the housing block, household id and sequential household member number). Household members will be sensitized on symptoms related to COVID-19, are asked to keep track of possible symptoms they may develop, and inform the study team by phone if a household member has a respiratory symptom, loss of smell or taste, so that upon assessment he/she can be asked to be swabbed for virological testing. In case a household member presents with symptoms which classify him/her as a possible case, a separate individual informed consent procedure for nasal swabbing will have to be performed prior to sampling. This ICF covers sampling for the first episode and any subsequent episode during the study period when nasal sampling would be indicated. Also during the baseline household visit, if full informed consent was provided (both for surveillance by the household head and for the sero- and social mixing survey by the individual household member), individual household members selected for the sero-survey will be asked for a baseline dried blood spot sample on filter paper, by administering a few blood drops through a finger prick.

Every two weeks a trained interviewer from the HDSS team will do calls to the head of the household or his representative, where during the call he will fill out a questionnaire (Household follow-up visit form) recording any respiratory symptoms, fever or other indicative sign of COVID-19 (at the time of the phone call, or in the last two weeks, if these symptoms go away), vaccination against COVID-19, and medical appointments that any family member has had.

Meanwhile (if applicable), demographic changes or changes in the chronic medical conditions of family members will be recorded. If a family member reports a respiratory sign or loss of smell or taste, with or without fever (possible case), a trained interviewer will do a home visit to this household.

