## 7. Statistical Analyses

### 7.1 Methods

All estimated transmission or clinical outcome indicators will be adjusted for the design effect, related to the selection of HDSS enumeration areas (clusters) within the source populations. Intraclass correlation coefficients can be deducted from previous studies in the HDSS. The results of the sero-survey and social mixing survey will additionally be adjusted for age-stratified sampling.

We will calculate a incidence rate of COVID-19 disease throughout one year, adjusting for the sensitivity of SARS-CoV-2 RT-PCR on nasal swabs by delay between symptom onset and testing. Using the longitudinal sero-survey data, determining the proportion of asymptomatics, we will be able to adjust the clinical incidence rate to a SARS-CoV-2 infection incidence rate, and determine the SARS-CoV-2 infection annual attack rate and the infection fatality risk by age group.

We will undertake three risk factor analyses: of SARS-CoV-2 infection, of COVID-19 disease (symptomatic infection), and of COVID-19 hospitalisation and death (severe disease). Using negative binomial regression, we will investigate the association with socio-demographic factors, clinical characteristics such as underlying medical conditions, and uptake of preventive measures. We also investigate the association between SARS-CoV-2 infection (from the sero-survey) and recent exposure, contact and mobility patterns (from the social mixing questionnaire).

We will assume everyone will be susceptible initially and basic and effective reproductive numbers ( $R_0$  and  $R_e$ ) will be calculated by the rate of change of incidence over successive serial intervals (time between onset of infection of index and onset of infection of infected).

We will use established methods (Cauchemez et al 2004; te Beest et al 2013) to estimate generation time distribution, ratio of transmissibility between symptomatic and asymptomatic cases, duration of

the infectious period, and the basic reproduction number, from the transmission data collected in households.

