### 10.2 Patient and/or community involvement

The HDSS community advisory board is being consulted on study procedures (eg. how and where to organise specimen collection), which has been successful and beneficial during previous studies integrated within the HDSS. Before the study starts, the HDSS staff will present the study to community leaders.

As soon as data are available and analysed after 3, 6 and 12 months, preliminary findings (COVID-19 incidence rate; case fatality; evolution of the reproduction number) will be presented to the HDSS community advisory board, health authorities and the national COVID-19 response team. Three months after evidence of local transmission, a larger preliminary analysis, including a first estimate of the infection attack rate and risk factor analysis will be presented to the same stakeholders, but also to community leaders.

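### Re from successive serial intervals has no correction for cases not yet detected, so if incidence is dated by onset, values in about the last 15 days before each data cut are biased downward

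*Combined protocol and SAP*

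**What the plan says.** Section 7.1 (Methods) obtains R0 and Re from case incidence: they "will be calculated by the rate of change of incidence over successive serial intervals". It defines the serial interval from onset in the index to onset in the person infected. Section 1.1 cites a "longer estimated serial interval of 3.96 days"; the study also plans to estimate its own.

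On routine case finding, section 5.1 states: "Every two weeks a trained interviewer from the HDSS team will do calls to the head of the household or his representative". Table 2 is on the same cycle ("One row corresponds to two weeks"). Routine contact is not the only route. Section 4.2 says: "Possible COVID-19 cases in the HDSS households will be detected through four entry points", and lists the two-weekly visit, a call by the patient, a call by the study team, and presentation at a health facility. The footnotes to Table 2 put PCR on the day after collection, with the result returned that day.

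Section 10.2 says that findings available after 3, 6 and 12 months, including the "evolution of the reproduction number) will be presented to the HDSS community advisory board", also go to the health authorities and the national response team.

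The only delay adjustment in section 7.1 concerns PCR sensitivity by time from onset to test. The protocol defines no data cut for Re, and does not say whether incidence is indexed by onset or by detection date.

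**The concern.** The contact cycle is about 3.5 times the serial interval (14 / 3.96). At a data cut, an illness that began a few days earlier is known only if the household has been contacted since, or if the person called or attended a facility. The newest serial interval is therefore counted less completely than the one before it, and a ratio of the two falls below the true Re for that reason alone. The PCR-sensitivity adjustment cannot repair this, because it acts on people who have been tested and the missing cases have not been.

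What is at stake is the end of the Re curve at each report. A flat or growing epidemic could appear to be declining.

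**Working it through.** **Plan's own figure.** Section 7.2 expects 2,790 detected cases and 1.50 per 100 person-months. 15,393 × 0.40 × 0.50 × 0.90 = 2,771, within 1% (2,790 is exact for a population of 15,500), and 2,771 / (15,393 × 12) = 1.50 per 100. The case stream behind Re is reproduced. The protocol gives no figure for reporting delay or for the precision of Re.

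**Inputs.**
- Serial interval S = 3.96 days (section 1.1).
- Contact cycle 14 days (section 5.1).
- Test lag L = 0 or 1 day (Table 2 footnotes).
- Time from onset to routine contact uniform on 0–14 days. This is an assumption; it fits households being worked through day by day (section 4.2: "we expect the HDSS interviewer to visit 6 households per working day on average").
- Share p found on the day of onset by call or facility: not given, so varied from 0 to 90%.

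**Formula.** The probability that an onset t days before the cut is known is

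F(t) = p × 1[t ≥ L] + (1 − p) × min(max((t − L)/14, 0), 1).

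C1, C2, … are the means of F over successive 3.96-day intervals counted back from the cut. With constant true incidence (Re = 1), apparent Re in interval k is C_k / C_(k+1).

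**Routine contact only, no lag.** C1 = 1.98/14 = 0.141; C2 = 5.94/14 = 0.424; C3 = 9.90/14 = 0.707; C4 = [(14² − 11.88²)/28 + 1.84]/3.96 = 0.959; C5 = 1. Apparent Re is 0.33, 0.60, 0.74, 0.96, then 1.00.

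**Routine contact only, one-day lag.** C1 = (2.96²/28)/3.96 = 0.079; C2 = 4.94/14 = 0.353; C3 = 8.90/14 = 0.636; C4 = 0.912. Apparent Re is 0.22, 0.56, 0.70, 0.91, then 1.00.

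**With a share p reported on the day of onset (latest value of Re).**

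| p | no lag | one-day lag |
|---|---|---|
| 0 | 0.33 | 0.22 |
| 25% | 0.63 | 0.48 |
| 50% | 0.80 | 0.61 |
| 75% | 0.92 | 0.69 |
| 90% | 0.97 | 0.73 |

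Example, p = 50% with the lag: C1 = 0.5 × (2.96/3.96) + 0.5 × 0.079 = 0.413; C2 = 0.5 + 0.5 × 0.353 = 0.676; ratio 0.61.

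If the faster routes instead take a mean of 2–3 days (exponential, assumed) plus the lag, then for p = 25–75% the latest value is 0.28–0.38 and the one before it 0.65–0.85.

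**Growing epidemic.** With true Re = 1.3, F(t) is weighted by exp(−rt), r = ln(1.3)/3.96. Routine contact only and no lag gives 0.42, 0.78 and 0.95 for the latest three values. With p = 50% and the lag, the latest reads 0.77.

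**Sampling noise.** 2,790/365 × 3.96 = 30.3 cases per interval. The 95% range of a ratio of two such counts around 1 is exp(±1.96 × √(2/30.3)), roughly 0.6 to 1.7.

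**Check of the remedy.** With routine contact only and the one-day lag, starting the series 15 days before the cut gives apparent Re = 1.00 in every interval. Starting it 14 days before gives 0.99 in the newest.

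**The case against.** A reader might infer that Re at each cut will certainly read far below 1, because cases are found only by contacts two weeks apart. The documents do not support that. Section 4.2 lists faster routes, section 3 adds an alert system through community leaders, section 10.6 offers airtime for calls, and contacts in up to 100 index-case households are swabbed soon after confirmation. The share by route is unknown, so values such as 0.22–0.33 are one end of a range. This objection stands on size; it does not remove the direction.

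The premises are also not fixed. The onset-to-onset definition makes onset dating the natural reading, but section 7.1 does not state it, and it does not say that the newest onsets are included. If incidence were dated by detection, this distortion would be replaced by a lag of up to two weeks. If all households were contacted on the day of the cut, there would be no truncation. The Synopsis mentions a rolling incidence rate, and smoothing would change the individual values.

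Sections 4.2 and 5.1 disagree on recall: the last week in one, the last two weeks in the other. Under a strict one-week window applied to onsets, routine detection stops rising at 7 days and the ratios become 0.34, 0.83 and 1.00 (no lag), so two intervals are affected rather than four.

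Noise is large. At 14% and 42% completeness the latest ratio rests on about 4 and 13 cases, and 0.33 has an approximate 95% interval of 0.11–0.99; the intervals around 0.60 and 0.74 include 1. That weakens any single reading, but noise goes both ways and truncation always points down.

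Finally, a reader might infer that the whole Re series is unreliable, or that decisions will follow from the false decline. About four intervals are affected, of some 23 at 3 months and 92 at 12 months, and section 10.2 calls the findings preliminary and states no decision rule. After the 3- and 6-month cuts the gap fills in; Table 2 shows no household visits after week 51, so the final tail gets no later routine contact.

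**Conclusion.** The concern holds in a conditional form. If Re is computed as section 7.1 describes, from onset-dated incidence that includes the newest onsets, its values in about the last 15 days before each of the three cuts are biased downward, and no planned adjustment addresses this. Earlier Re values and R0 from the early growth phase are not affected.

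The size depends mainly on the unstated share of cases reaching the study by the faster routes. At true Re = 1 the latest value runs from 0.22 (routine contact only, one-day lag) to 0.97 (90% reported on the day of onset, no lag). With the protocol's own next-day PCR it stays at or below 0.73 across the shares examined. These figures assume contacts spread evenly over 14 days, a 3.96-day serial interval, a two-week recall window and no smoothing. The numbers illustrate the bias; they do not predict what the study will report.

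**What to change.** In section 7.1, state that incidence for Re is indexed by symptom-onset date, define the data cut for each report, and at each cut do one of the following:

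- End the Re series at least 15 days before the cut (14-day contact cycle plus next-day PCR).
- Nowcast the recent onset counts with the observed onset-to-result delay distribution, estimated by entry point, and carry its uncertainty into the interval for Re.

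Also reconcile the symptom recall windows in sections 4.2 and 5.1, because the window determines which onsets a contact can capture and therefore the delay distribution.

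The cost is analysis wording and a short program; no extra visits or samples are needed. Onset date, test date and entry point have to be available for each case. The downside is that the newest reported Re is about two weeks old, or has a wider interval.

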Immune factors may affect community transmission. Cross reactivity with existing endemic coronaviruses, (CoVs 229E, NL63, HKU1,OC43), two of which are related beta-coronaviruses (HKU1,OC43), could result in protection from infection and/or disease. Many models assume a person can no longer be infected once recovered (Fig 1). However, immunity to coronaviruses is unclear. Antibody titer to SARS-CoV-1 infection waned over a period of several months in recovered patients (Liu et al 2006), but unclear if this means waning protection. Additionally, endemic human coronaviruses existing neutralising antibodies may not sufficiently protect against reinfection (Callow et al 1985), while some reports of reinfection with SARS-CoV-2 have been reported, though none fully documented.

[figure not shown]

Fig 1. Susceptible-Infected-Recovered Model

In the first few weeks of 2021, vaccines under WHO's Emergency Use Listing have begun to be used in several countries and plans exist to roll out one or more vaccine types in Mozambique. Vaccine effectiveness studies are key to better understand how these vaccines perform in different settings, especially since the emergence of SARS-CoV-2 variants circulating in Mozambique against which several current vaccines may not protect.

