### 3. Study Design

Prospective cohort study (observational). We will use the established HDSS to set up population-based COVID-19 surveillance in a household cohort. From any individual in this population reporting any respiratory sign (symptom or lowered peripheral oxygen saturation) or loss of smell or taste, with or without fever, we will collect a respiratory specimen and test these for SARS-CoV-2 virus by PCR, during 12 months. These cases will be identified through bi-weekly household visits, through an alert system involving community leaders and HDSS interviewers, or when presenting with symptoms at healthcare centres or at the referral hospital. Identified healthcare facilities will then alert the study team if a possible case from the HDSS population is consulted or admitted, if the patient agrees. Demographic, epidemiological and clinical data (comorbidities, medication, obesity, HIV, TB, smoking) of possible cases and of the source population will be recorded at baseline; recent illness, potential risk exposure of each household member (including duration and type) to SARS-CoV-2 positive individuals, uptake of measures to reduce exposure/transmission, and barriers to the uptake of such measures, will be

recorded/updated during every household visit. COVID-19 vaccination status will be recorded from possible cases and compared to that of a subset of the population, in a case-cohort design to determine vaccine effectiveness against symptomatic COVID-19.

An age-stratified serial sero-survey will be conducted at baseline in a subset of the population in the population-based COVID-19 surveillance, and at 3, 6 and 12 months, after confirmation of community transmission. Recording vaccination status of all sero-survey participants, we will determine vaccine effectiveness against SARS-CoV-2 seroconversion in a cohort design.

Household transmission will be specifically investigated, by investigating contact history, vaccination status, and the presence of SARS-CoV-2 virus and serology among household members twice during the month after the symptom onset of a household index case.

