An **age-stratified random sample** of that population will be selected for the **repeated sero- and social mixing survey**. By age stratum (0-17 years; 18-50 years; >50 years) we randomly select 800 individuals (simple random sample per age stratum; 2400 in total) from the Polana Caniço HDSS population (regardless of infection or disease status or history), from whom during home visits dried blood spots will repeatedly be collected at 0, 3, 6 and 12 months, vaccination status against COVID-19 will be recorded, and who will be asked to respond to a social mixing questionnaire. A HDSS sampling frame of all individual participants in the HDSS with socio-demographic data and unique identifiers, is available, and will be used to select a simple random sample of individuals by age group.

When a member of a household with no prior widespread transmission (see exclusion criteria) tests SARS-CoV-2 positive, we will revisit the household twice for a household transmission investigation: as soon as possible after the result of the household index case (baseline), and once again one month after symptom onset of the household index case. An initial contact report form will be filled in as soon as possible, ideally within 24 hours, after laboratory confirmation of the primary case in the household. Respiratory and dried blood spot samples will be collected of everyone considered resident (as defined by the HDSS) in the household and who has been in contact with the SARS-CoV-2 positive individual, regardless of age and presence or absence of symptoms. Respiratory samples will be analysed by RT-PCR for SARS-CoV-2 to assess presence of virus and viral load. The dried blood spots for serology on the Luminex assay. Data will be collected on household exposures of contacts and vaccine receipt. Symptomatic household contacts will be tested whenever symptoms appear, as part of the population-based surveillance. This is planned for upto 100 household index cases.

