We will derive brand-specific total vaccine effectiveness against infection and against disease, in respectively a case-cohort design and a cohort design. Total vaccine effectiveness is the protection of vaccinees due to direct effects and added protection of vaccinees owing to vaccination of their neighbors or contacts, while overall vaccine effectiveness considers protection of an entire population, irrespective of the vaccination status of its individual members, due to the combination of total protection and protection of non-vaccinees due to vaccination of their neighbors or contacts (Ali et al 2015). To derive total vaccine effectiveness against infection, we will compare the proportion of sero-survey participants who seroconverted in the past 3 months among vaccinated against the proportion in non-vaccinated, adjusting for age and sex and other confounders. To derive total vaccine effectiveness against disease, we will compare the odds of vaccination among symptomatic confirmed SARS-CoV-2 cases detected through the population-based surveillance with the odds of vaccination among sero-survey participants who did not seroconvert in the past 3 months, in a case-cohort design. We will also explore overall vaccine effectiveness against disease using regression models comparing housing blocks with different levels of vaccination coverage among sero-survey participants.

We will estimate the conventional data-based secondary attack rate, which is the proportion of seroconversion among identified household contacts. However, these are not necessarily all secondary infections from the household index case, and could be tertiary. Therefore we will also derive a model-based secondary attack rate, estimating the number of actual secondary infections of the household index case. To do so, we could use a chain-binomial statistical model, as described by Jing et al (doi:10.1016/S1473-3099(20)30471-0), with an expectation-maximisation algorithm to account for (a) uncertainty in the infection time of asymptomatic infections, for (b) an incubation and infectious period distribution, as described in literature, and consider (c) the timing of symptom onset in

symptomatic household contacts and (d) the age-specific proportion of asymptomatic infections as estimated from the active population-based surveillance and sero-survey.

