## 7.2 Sample size and power

Assuming a 40% annual attack rate, 50% symptomatic infections (cases), 2% overall case fatality risk, of which 90% are identified by the active population surveillance, 2790 COVID-19 cases and 56 deaths will be identified through the study period. The average incidence rate of the HDSS population would then be 1.50 cases per 100 person months with lower and upper 95% confidence interval limits 1.45 and 1.56. The overall case fatality risk would have as lower and upper 95% confidence interval limits at 1.53 and 2.58%.

To determine the infection attack rate from a simple random population sample of three age strata (comparable in size), with +/-3% confidence limits, 95% confidence interval, assuming the attack rate may reach 40% towards the end of the study period, samples from 800 individuals per age stratum per round will need to be collected.

Assuming the household secondary attack rate to be close to 17% (Fung et al, Clin Infect Dis, 2020) and a median household size of 7.3 (based on HDSS data), a 5% confidence limit and a design effect of 3, 642 household members will need to be enrolled, or 100 households. The WHO also recommended to include 100 households in household transmission investigations.

Assuming 20% vaccination coverage among the 2400 sero-survey participants, 5% of sero-conversion over 3 months and 10% of seroconversion over 6 months, a 95% two-sided confidence interval and an anticipated crude total vaccine effectiveness of 50%, there will be 66% power to observe this effect after 3 months and 97% power after 6 months.

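### The contrast for vaccine effectiveness against seroconversion is not tied to vaccination status at the start of the interval, so during roll-out infections that precede vaccination can count in the vaccinated arm

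*Combined protocol and SAP*

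**What the plan says.** Section 7.1 (Methods) defines total VE against infection by a comparison of cumulative proportions: "we will compare the proportion of sero-survey participants who seroconverted in the past 3 months among vaccinated against the proportion in non-vaccinated". The stated adjustment is "adjusting for age and sex and other confounders". Section 3 (Study Design) describes the same analysis: "Recording vaccination status of all sero-survey participants, we will determine vaccine effectiveness against SARS-CoV-2 seroconversion in a cohort design".

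On data capture, section 4.2 provides that "dried blood spots will repeatedly be collected at 0, 3, 6 and 12 months, vaccination status against COVID-19 will be recorded". Section 5.1 adds a call to the household head or a representative every two weeks, which asks about "vaccination against COVID-19, and medical appointments that any family member has had". It does not mention date, dose number or brand.

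On timing, section 1.1 notes early in 2021 that "plans exist to roll out one or more vaccine types in Mozambique", and the Synopsis dates the study December 2020 to December 2021.

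Section 7.2 (Sample size and power) starts from "Assuming 20% vaccination coverage among the 2400 sero-survey participants, 5% of sero-conversion over 3 months and 10% of seroconversion over 6 months". It anticipates a crude total VE of 50% and states 66% power at 3 months and 97% at 6 months.

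The objectives in section 2, Table 1 and sections 3, 4.2, 5.1, 7.1 and 7.2 give no rule for status at the start of the interval, no lag after a dose, no required number of doses, no handling of people vaccinated mid-interval and no person-time analysis.

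**The concern.** The outcome accumulates over a closed interval, while the exposure is a label with no date attached. If the label is read at the closing blood spot, someone infected in week 2 and vaccinated in week 10 is a vaccinated seroconverter. Someone vaccinated a week before the closing draw is counted as vaccinated for the whole three months. Adjusting for age, sex and other confounders cannot move a pre-vaccination infection out of the vaccinated arm, because the fault lies in how exposure time is assigned.

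VE against seroconversion is a named secondary objective, and brand-specific figures are meant to inform the national response. A vaccine that works could look poor in the interval when it is introduced, which is when the estimate would draw most attention. If the rule is fixed only after the data are seen, it can also be chosen with the results in view.

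**Working it through.** **Inputs.** From 7.2: 2,400 participants, 20% coverage (480 vaccinated, 1,920 not), 5% seroconversion over 3 months, 10% over 6 months, VE 50%. Assumptions of this review, not in the documents: infections and in-interval doses are spread evenly over a 91-day interval, and any lag to protection is 14 days.

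**The plan's own power.** A pooled normal test of 2.5% against 5% (480 v 1,920) gives 68.8%, against a stated 66%. For 5% against 10% it gives 96.2%, against 97%. Each stated figure comes within 2 points under some standard variant, but none of those tried matches both. Neither is called wrong here, and the point does not depend on them.

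**Bias.** Let f be the share of vaccinees vaccinated before the interval, and p the mean protected fraction of the interval for the rest.

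- Risk ratio = f(1 − VE) + (1 − f)(1 − VE·p), so observed VE = VE·[f + (1 − f)p].
- No lag: p = 1/2. With the lag: p = (1 − 14/91)²/2 = 0.358.
- One quarter within the interval (f = 0.75): 0.5 × (0.75 + 0.25 × 0.5) = 0.4375; with lag 0.420.
- One half (f = 0.5): 0.5 × (0.5 + 0.5 × 0.5) = 0.375; with lag 0.339.
- All (f = 0): 0.5 × 0.5 = 0.25; with lag 0.179. Without lag, the vaccinated arm's risk is 5% × 0.75 = 3.75% instead of 2.5%.

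A constant-hazard model (hazard halved after vaccination) checks this and gives the power of the contrast as written:

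| Vaccinated within interval | VE, formula | VE, formula with lag | VE, constant hazard, no lag | Power, 3 months, constant hazard |
|---|---|---|---|---|
| none | 50% | 50% | 49% | 67% |
| one quarter | 44% | 42% | 43% | 53% |
| one half | 38% | 34% | 37% | 39% |
| all | 25% | 18% | 25% | 19% |

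In the last row, about 66% of the infections in the vaccinated arm precede vaccination (roughly 0.5 / (0.5 + 0.25)). For a 6-month interval at 10% risk, the constant-hazard VE runs from 49% down to 24%. The last gap between blood spots, from month 6 to month 12, is that long.

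**The opposing effect.** Suppose that, in the all-within case, a fraction q of people infected before their planned dose are then not vaccinated in the interval. Simulation gives VE of 25% (q = 0), 39% (0.25), 49% (0.45), 52% (0.50) and 77% (1.0). The two effects cancel near q = 0.46. Section 7.2 assumes 50% of infections symptomatic and 90% of those detected, so about 0.50 × 0.90 = 45% would be known through surveillance. Fewer would be known after the switch in Table 1 to testing 1 in 10 possible cases. People could also defer on symptoms alone, which on the plan's figure allows q up to 0.50.

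**Power with correct timing.** If all 480 are vaccinated evenly within the interval, vaccinated follow-up is about 480 × 0.5 = 240 person-intervals, against 1,920 + 240 = 2,160 unvaccinated. The same pooled test gives about 38% power at 3 months and 76% at 6 months.

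**The case against.** The strongest reply is that the plan is silent on timing and does not rule it out. Section 3 calls this a cohort design, which fits status fixed before follow-up. Status is recorded at repeated rounds, so the opening round can supply it, and the two-weekly calls place vaccination approximately. All of that stands: a reader might infer that the sponsor has decided to ignore timing, and the text does not say so. But the contrast that 7.1 does state gives a biased result if applied literally, and no other section corrects it.

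A reader might also infer that VE must be pulled toward zero. The misassigned infections do act that way, but deferral acts against them, so the net direction is not settled.

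The 25% and 18% figures are the extreme of the range. They need every vaccinee in the contrast to have been vaccinated inside that one interval. This is natural for the interval in which roll-out begins and unlikely later. The documents give no roll-out timetable.

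Finally, a reader might infer that the 50% in 7.2 is wrong. That section calls it crude, which can mean the value the unadjusted contrast is expected to show. The documents do not settle this. The calculation above takes 50% as the true effect.

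**Conclusion.** The point holds as an unspecified exposure definition with a material consequence. If three-month seroconversion is compared by vaccination label alone, a true VE of 50% reads somewhere between 44% and 25% as the share vaccinated within the interval rises from one quarter to all (42% to 18% with a 14-day lag). The bias is nil for anyone vaccinated before the interval.

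The size rests on the plan's 5% risk, on even spread of infections and doses, on no deferral, and on seroconversion marking infection and not the response to vaccine. With deferral by close to half of those infected beforehand, the error roughly cancels, and beyond that it reverses. Such a cancellation would be accidental and could not be checked from the planned analysis. The primary outcomes in Table 1 are unaffected.

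**What to change.** **In 7.1.** Restrict the analysis to participants seronegative at the opening blood spot. Treat vaccination as time-varying: split follow-up at the vaccination date plus a prespecified lag, and treat seroconversion as interval-censored between the two draws. Define the interval by the draws themselves, since the last gap is six months.

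**Sensitivity analysis.** Classify both arms by status at the opening blood spot. This removes the misassigned infections but dilutes the comparator. If 20% of it were vaccinated evenly in the interval, its risk would be 5% × (1 − 0.2 × 0.25) = 4.75%, and VE would read 1 − 2.5/4.75 = 47%. It also has no vaccinated arm in the interval when roll-out begins.

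**What to avoid.** The comparator should not be defined as having no dose up to the closing draw, because that conditions on later status. If 20% were due to be vaccinated evenly in the interval and all those infected first deferred, comparator risk would be (0.8 × 0.05 + 0.2 × 0.05 × 0.5)/(0.8 + 0.005) = 5.6%, and VE would read 1 − 2.5/5.6 = 55%.

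**Forms.** Add vaccination date, dose number and brand to the existing two-weekly and sero-survey forms. Section 5.1 as written does not show that these are captured.

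**In 7.2.** Restate power for the vaccinated follow-up expected under this definition, with the assumed timing of roll-out.

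**Cost.** Analysis text, a few form fields, and less vaccinated follow-up with lower precision in the first interval after introduction.
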